8.6. Exploratory Efficacy Analyses (Part 1)

8.6.1. Annualized Change in eGFR (2021 CKD-EPIcr-cys_R)

This analysis is based on the annualized change in eGFR (2021 CKD-EPIcr-cys_R) with restriction (defined in Section 8.2 Primary Efficacy Analysis except that in this analysis the eGFR values will be calculated from 2021 CKD-EPIcr-cys_R) on the PEAS. An ANCOVA model with fixed effects for treatment group (0=placebo, 1=lixivaptan) and the randomization stratification factors (CKD stage [CKD2 versus CKD3/4] and Mayo Clinic ADPKD Image Classification [1C, 1D, or 1E]) and the baseline eGFR as a covariate.

SAS code from the primary efficacy endpoint analysis can be used (Section 8.2).

This analysis assumes that data are missing at random.

8.6.2. Annualized Percent Change in Height-adjusted Liver Volume (htLV)

This analysis is based on the annualized percent change in htLV from baseline to 28 days after the last dose of the study drug, i.e., Visit 25 during the Follow-up Period I after Week 52 for ontreatment completers or, for participants who discontinue study drug treatment prior to Week 52 [Visit 22], during the Follow-up Period 28 days following study drug treatment discontinuation. Baseline htLV is the one obtained at Screening (Visit 1a). Missing data will not be imputed for this analysis.

In order to reduce the variability in the time of post-baseline MRI acquisition, elapsed time from baseline to post-baseline MRI will be treated as a continuous variable, expressed as years from date of Baseline MRI acquisition to date of MRI acquisition visit (date of MRI visit – date of Baseline MRI + 1). In addition, in order to reduce heterogeneity in variance and achieve linearity over time, log10 transformation will be applied to the htLV data.

An ANCOVA will be used to analyze the log-transformed htLV data on the PEAS to estimate annualized percent change in htLV by time. The model will include fixed effects for treatment group (0=placebo, 1=lixivaptan), the randomization stratification factors (CKD stage [CKD2 versus CKD3/4] and Mayo Clinic ADPKD Image Classification [1C, 1D, or 1E]), baseline htLV, (elapsed) time, and treatment group-by-time interaction as a covariate.

Example SAS code in Section 8.3.2 for the htTKV analysis can be used to analyze the htLV when the log-transformed htTKV data are replaced by the log-transformed htLV data.

A significance level of 0.01 (two-sided) will be used to declare statistical significance of treatment effect at the final analysis. Antilog (with a base of 10) of the treatment effect and 99% confidence intervals (99% CIs) derived from the model (in a log10 scale) provide a ratio of geometric means of the relative change (ratio) from baseline in htLV (i.e., 100% plus annualized percent change).

8.6.3. Urine Osmolality

Descriptive statistics for the change from baseline (Visit 2) in morning spot urine osmolality will be presented by treatment group for the PEAS. The number (%) of participants who show suppressed urine osmolality in each treatment group, defined by 2 levels of spot urine osmolality \leq 250 mOsm/kg and \leq 300 mOsm/kg will be summarized descriptively at each time point.

8.7. Key Comparison Endpoint Analysis (Part 2)

All the eGFR assessments for this analysis are calculated from the 2021 CKD-EPI equation (2021 CKD-EPIcr_R).

Descriptive statistics will be presented by treatment cohort for the key comparison analysis of annualized change in eGFR from baseline (mean of 3 eGFR values obtained at off-treatment visits after Week 52 during Follow-up Period I) to final assessment (mean of 3 eGFR values obtained during Follow-up Period II after Week 104 for on-treatment completers or, for participants who discontinue study drug treatment prior to Week 104 [Visit 42], 8 to 28 days following study drug treatment discontinuation) for the P2EAS.

To assess durability and continuation of treatment effect observed in Part 1, the mean annualized change from baseline by treatment cohort for Part 2 will be presented along with Part 1 results for the participants in that treatment cohort.

In addition, descriptive statistics for the annualized change from baseline in the eGFR to final assessment will be presented for all the participants in P2EAS (overall).

8.8. Sensitivity Analysis of the Key Comparison Analysis (Part 2)

All the eGFR assessments for this analysis are calculated from the 2021 CKD-EPI equation (2021 CKD-EPIcr R).

Descriptive statistics will be performed for all available annualized changes from baseline (the mean of the 3 off-treatment eGFR values obtained after Week 52 in Part 1) to the mean of the 3 off-treatment eGFRs after Week 104 for the P2EAS. Descriptive statistics will be presented by treatment cohort and overall along with Part 1 results for the same participants in each treatment cohort.

8.9. Other Comparison Analyses (Part 2)

8.9.1. Annualized Rate of Change (Slope) in eGFR

All the eGFR assessments for this analysis are calculated from the 2021 CKD-EPI equation (2021 CKD-EPIcr_R).

All the observed changes from baseline (mean of the 3 eGFR values obtained at off-treatment visits after Week 52 in Part 1) to all visits with on-treatment eGFR values during the Maintenance Treatment Period visits, i.e., Visit 30 (Week 56) up to Visit 42 (Week 104), while on study drug treatment in the P2EAS will be utilized for determining the annualized rate of change (slope) in eGFR. Any eGFR values obtained after 1 or more days off of study drug treatment during the Maintenance Treatment Period are excluded from the analysis.

To determine the annualized rate of change (slope) in eGFR, the average of observed changes from baseline at each visit by treatment cohort and overall will be calculated. The annualized rate of change (slope) in the eGFR will be calculated by:

The annualized rate of change (slope) in eGFR = (-6 x mean change at Visit 30 -5 x mean change at Visit 31 -4 x mean change at Visit 32 -3 x mean change at Visit 33 -2 x mean change at Visit 34 -1 x mean change at Visit 35 -0 x mean change at Visit 36 +1 x mean change at Visit 37 +2 x mean change at Visit 38 +3 x mean change at Visit 39 + 4 x mean change at Visit 40 + 5 x mean change at Visit 41 + 6 x mean change at Visit 42)/14.

The annualized rate of change (slope) from baseline in eGFR in Part 2 will be presented by treatment cohort and overall for participants in the P2EAS along with the annualized rate of change (slope) from baseline at Part 1 for the participants in each treatment cohort.

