8.7 Other Comparison Analyses

8.7.1 Annualized Rate of Change (Slope) in eGFR on Treatment

In order to assess the linear effect (slope) of lixivaptan based on the on-treatment eGFR data in Part 2, an analysis utilizing a MMRM will be performed on the observed changes from baseline (mean of the 3 eGFR assessments obtained during Follow-up Period I) to Weeks 52 to 104 (Visit 29 to Visit 42) of the Maintenance Treatment Period in eGFR. The MMRM will include visit, and randomization stratification factors as fixed effects, and baseline (Follow-up Period I in Part 1) as a covariate, and the baseline-by-visit interaction. An unstructured variance-covariance matrix is assumed for the repeated measures. The estimated annualized rate of change (slope) from this analysis will be compared to the corresponding results in Part 1.

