2.2.3. Secondary Objectives

- To assess the rate of change (slope) in on-treatment eGFR in Part 2 in participants treated with lixivaptan in Part 1 and Part 2;
- To assess the effect of lixivaptan on height-adjusted TKV (htTKV) as measured by MRI in Part 2 in participants treated with lixivaptan in Part 1 and Part 2.

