CLASS TREATMENT VISIT CKD_STAGE MAYO_CLASS USUBJID;

MODEL CHANGE = TREATMENT BASELINE VISIT VISIT*TREATMENT BASELINE*VISIT CKD_STAGE

MAYO_CLASS /SOLUTION;

REPEATED VISIT/TYPE=UN SUB= USUBJID;

ESTIMATE "Lixivaptan Annualized Slope" VISIT -6 -5 -4 -3 -2 -1 0 1 2 3 4 5 6

VISIT*TREATMENT 0 0 0 0 0 0 0 0 0 0 0 0 -6 -5 -4 -3 -2 -1 0 1 2 3 4 5 6/DIVISOR=14;

ESTIMATE "Placebo Annualized Slope" VISIT -6 -5 -4 -3 -2 -1 0 1 2 3 4 5 6

VISIT*TREATMENT -6 -5 -4 -3 -2 -1 0 1 2 3 4 5 6 0 0 0 0 0 0 0 0 0 0 0 /DIVISOR=14;

ESTIMATE "Treatment Difference in Annualized Slope"

VISIT*TREATMENT 6 5 4 3 2 1 0 -1 -2 -3 -4 -5 -6 -6 -5 -4 -3 -2 -1 0 1 2 3 4 5 6/DIVISOR=14;
```

A linear contrast of the treatment slope differences for visits will be used for this analysis.

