This study has been early terminated by the Sponsor. Due to only 5 participants being randomized into double-blinded, randomized treatment period in Part 1 and all being prematurely terminated in Part 1 of the study, no statistical analyses will be performed and only a limited set of summary tables will be generated along with the study data listings to facilitate the creation of a synoptic clinical study report.

13. Tables, Listings, and Figures

All listings, tables, and figures will have

- A header showing the sponsor company name, protocol, and page number
- A footer showing the file name and path, the source of the data (ADaM dataset or listing number) and date/time created.

The layouts of tables, listings, and figures are presented in SAP Mock Tables, Listings and Figures. These layouts incorporate all the appropriate table titles, table numbers, and footnotes.

14. Mock Tables, Listings, and Figures

The table, listing, and figure shells will be provided in a separate document.

15. Changes from Protocol

Any analyses that deviated from the study protocol are documented below.

Text in Protocol	Change in SAP	Justification
None	Placebo Run-in Safety Set, Lixivaptan Titration Safety Set, ITT, mITT, PPAS, Lixivaptan Treated Safety Set are added in Section 5 Analysis Population	Those analyses population will be needed to summarize the efficacy or safety data
Analysis safety and efficacy sets for Part 2 in Section 5 Analysis Populations	Re-define as two analysis sets: P2SS for safety and P2EAS efficacy, but summary in Part 2 will be presented by treatment cohort	The revised analysis populations are more appropriate for safety and efficacy analyses in Part 2.
LV for analysis	htLV for analysis	To reduce the variance of LV and normalize to participant's height
Annualized change from baseline in htTKV (htLV)	Annualized percent change from baseline in htTKV (htLV)	Anti-log of annualized change from baseline based on the log- transformed htTKV (htLV) implies the annualized ratio of htTKV (htLV) at the evaluated timepoint to baseline htTKV (htLV). This ratio minus one as expressed as percentage will represent annualized percent change from baseline in htTKV (htLV), but not annualized change from baseline in htTKV (htLV).
None	Lixivaptan treated safety summaries have been added in Section 9.6	To add overall safety after randomization during the entire study for all lixivaptan-treated participants during double-bind phase and/or open-label phase.

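### The SAP swaps the protocol's MMRM for raw visit means in the Part 2 on-treatment eGFR slope without listing the change, and its Part 1 example code gives per-arm slopes at baseline eGFR 0

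*SAP*

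**What the plan says.** **Part 2 slope.** Protocol 8.7.1 states that "an analysis utilizing a MMRM will be performed on the observed changes from baseline". It adds: "The MMRM will include visit, and randomization stratification factors as fixed effects, and baseline (Follow-up Period I in Part 1) as a covariate", together with baseline-by-visit and an unstructured covariance. The resulting slope is to be compared with Part 1.

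SAP 8.9.1 takes on-treatment values from Visits 30 to 42 and drops any value obtained one or more days off drug. Then "the average of observed changes from baseline at each visit by treatment cohort and overall will be calculated". The visit means are weighted -6 to 6 and divided by 14. There is no model, covariate or standard error. The result is shown "along with the annualized rate of change (slope) from baseline at Part 1 for the participants in each treatment cohort", with no statement of how that Part 1 slope is estimated. The quantity serves a named Part 2 secondary objective in SAP 2.2.3: "To assess the rate of change (slope) in on-treatment eGFR in Part 2".

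SAP Section 15 (Changes from Protocol) says: "Any analyses that deviated from the study protocol are documented below". Its rows cover added populations, redefined Part 2 analysis sets, height-adjusted liver volume, percent change in kidney and liver volume, lixivaptan-treated safety summaries and removal of the blinded sample size re-estimation. None concerns the slope estimator. The move of the first visit from Visit 29 (protocol) to Visit 30 (SAP) is not listed either.

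**Part 1 slope.** SAP 8.3.1 keeps the MMRM. Its example code has "MODEL CHANGE = TREATMENT BASELINE VISIT VISIT*TREATMENT BASELINE*VISIT CKD_STAGE" and the Mayo class. The two per-arm ESTIMATE statements give "VISIT -6 -5 -4 -3 -2 -1 0 1 2 3 4 5 6" and matching `VISIT*TREATMENT` coefficients, but none for `BASELINE*VISIT`.

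**The concern.** A mean of the values observed at a visit describes only those still on drug then. If stopping depends on earlier eGFR, the later means come from a slower-declining group and the contrast understates the decline. An MMRM uses the earlier values of those who stopped and is valid when data are missing at random.

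The route to bias is one the sponsor anticipates. Protocol 4.2.5 lists lack of efficacy, including need for dialysis or transplantation, as a reason for stopping, and SAP 6.1.4 singles out lack-of-efficacy drop-out for sensitivity analysis.

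A reader will set the Part 2 slope beside the Part 1 slope as evidence of durability. If the two come from different estimators, part of any difference is method. If the Part 1 arm slopes come from the example code, they also refer to a baseline eGFR that no participant can have.

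**Working it through.** **1. The contrast scaling is right.** With c = -6, …, 6 and weeks 4, 8, …, 52, the sum of c × week is 728, and 728/52 = 14, as SAP 8.3.1 states. The c sum to 0, so weeks 56 to 104 give the same 728 and 14. The divisor in SAP 8.9.1 is therefore correct. Only the means fed into it are in question.

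**2. Part 2 inputs.** From the documents: 900 randomized to lixivaptan and 90% expected to continue, so 0.90 × 900 = 810; 13 visits. Assumed, because the documents give no values: true slope -3.0 mL/min/1.73 m² per year, visit SD 4, slope SD 3 or 5, and drop-out log-odds rising 0.25 per mL/min of last observed decline. As a plausibility check, slope SD 5 with three-value means at both ends gives sqrt(5² + 4² × (1/3 + 1/3)) = 5.97, near the planned SD of 6.20.

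**3. Part 2 results** (150 simulated cohorts per scenario, Monte Carlo SE 0.02):

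| Slope SD | Drop-out | Raw means | MMRM | Raw-mean error |
|---|---|---|---|---|
| 5 | none | -3.02 | -3.02 | -0.02 |
| 5 | random, 8% | -3.04 | -3.04 | -0.04 |
| 5 | random, 16% | -3.00 | -3.01 | 0.00 |
| 3 | decline-related, 8% | -2.91 | -3.01 | 0.09 |
| 3 | decline-related, 16% | -2.81 | -3.01 | 0.19 |
| 5 | decline-related, 9% | -2.66 | -2.97 | 0.34 |
| 5 | decline-related, 18% | -2.41 | -3.01 | 0.59 |

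**4. A second simulation varied the steepness.** It also gave each participant a persistent offset (SD 4), with slope SD 3, visit SD 3 and the same true slope. The likelihood estimate stayed between -3.00 and -3.02 throughout.

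| Log-odds per mL/min | Raw means, 10% drop-out | Raw means, 20% drop-out |
|---|---|---|
| 0 | -3.01 | -3.02 |
| 0.1 | -2.78 | -2.54 |
| 0.2 | -2.58 | -2.14 |
| 0.4 | -2.30 | -1.68 |

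**5. Part 1 per-arm code.** Let s be an arm's slope at mean baseline m, and g the change in annual slope per unit of baseline eGFR. The slope at baseline b is s + g(b - m). Leaving `BASELINE*VISIT` without coefficients sets b = 0, so the code returns s - g·m. (The lixivaptan row is read with 13 leading zeros; the extracted text shows 12, which may be a reading artefact.)

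- For an assumed g of ±0.02 and m of 45 to 65, the offset is 0.02 × 45 = 0.9 to 0.02 × 65 = 1.3 per year in either direction. It is zero if g = 0.
- Simulated with 900/450 and a true lixivaptan slope of -3.0, the coded slope averages -4.18 for g = +0.02, -1.85 for g = -0.02 and -3.01 for g = 0.
- Between arms, (s_L - g·m) - (s_P - g·m) = s_L - s_P. The simulated difference stays at 1.40 to 1.41.
- Precision: if baseline is uniform on 25 to 90 (mean 57.5, SD 18.76), the SE is multiplied by sqrt(1 + (57.5/18.76)² × n_arm/N). That is 2.69 for lixivaptan (n_arm/N = 2/3) and 2.03 for placebo (1/3).

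The kidney-volume code in SAP 8.3.2 does supply the baseline mean in its per-arm ESTIMATE statements, so the omission in 8.3.1 is inconsistent with the SAP's own practice.

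**The case against.** The Part 2 slope is descriptive, comes from a single-arm open-label phase and carries no test. Protocol 8.14 lets the SAP modify the plan and requires an amendment only for major changes to the primary analysis. SAP 8.9.1 states its estimator exactly. SAP 8.12 allows further exploratory analyses for differing exposure patterns, and SAP 8.7 and 8.8 give off-treatment summaries that include early stoppers with follow-up. The protocol never says how a slope is extracted from its categorical visit terms.

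The size also depends on an assumed steepness. At about 10% drop-out with slope SD 3 to 5 and visit SD 4, a separate check gave an error of 0.05 to 0.10 at 0.05 log-odds per mL/min, 0.11 to 0.19 at 0.10 and 0.27 to 0.48 at 0.25. Protocol 4.2.5 says mild creatinine rises should not lead to withdrawal, which argues against a steep dependence. The anchor to 6.20 does not single out slope SD 5: slope SD 3 with visit SD 6 gives sqrt(3² + 6² × 2/3) = 5.74. The Part 1 code is labelled an example and leaves the tested difference intact.

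Much of this stands. There is no breach of the amendment rule, the size is uncertain and the main analyses are untouched. It does not remove the point: the change is undeclared, it gives up the missing-at-random handling the protocol had planned, and SAP 8.12 is optional. The steepness alters the size of the error but not its direction.

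**Conclusion.** Both points hold, and the plan should be changed.

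The Part 2 slope in SAP 8.9.1 departs from Protocol 8.7.1 without an entry in Section 15 and is open to bias in the favourable direction. The error is nil if drop-out is unrelated to outcome and 0.09 to 0.59 mL/min/1.73 m² per year in the main scenarios. It can be smaller with weaker dependence and larger with a persistent between-participant offset. For scale, the planned treatment difference is 1.40 in absolute size. These sizes rest on assumed drop-out, variance and slope values, so confidence in them is moderate.

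The Part 1 per-arm slopes from the example code refer to baseline eGFR 0. They are shifted by mean baseline × g, with sign unknown, and have roughly two to three times the standard error under the uniform-baseline assumption.

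Unaffected are the between-arm slope test in Part 1 and the main durability analysis in SAP 8.7, which uses off-treatment change. SAP Section 12 records that only 5 participants were randomized and that no statistical analyses will be performed, so this concerns the plan as written and no reported result.

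**What to change.** - **SAP 8.9.1:** use the protocol's MMRM (visit, stratification factors, Part 2 baseline, baseline-by-visit, unstructured covariance). Fit it by cohort, or add cohort and cohort-by-visit terms and say that these are additions, since the protocol model has none. Apply the -6 to 6 over 14 contrast at the mean baseline and report confidence intervals.
- **Part 1 comparator:** state that the Part 1 slope shown beside it uses the same estimator in the same participants.
- **SAP 8.3.1 code:** centre baseline eGFR, or give `BASELINE*VISIT` coefficients equal to mean baseline times -6 to 6, with DIVISOR=14, in the two per-arm ESTIMATE statements.
- **SAP Section 15:** list any departure that remains, including the change of first visit. If raw means are kept, give the reason.

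The cost is SAP wording, one table row and a few lines of code.

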8.9.2. Annualized Percent Change from Baseline in htTKV

The annualized percent change from baseline in htTKV is estimated by the annualized change in log10-transformed htTKV, annualized by the elapsed time (years) between two dates of MRI taken, from baseline to 28 days after the last dose of the study drug, i.e., Visit 45 during the Follow-up Period II after Week 104 for on-treatment completers or, for participants who discontinue study drug treatment prior to Week 104 [Visit 42], during the Follow-up Period 28 days following study drug treatment discontinuation. Baseline htTKV is the one obtained at off treatment follow-up Visit 25 after Week 52 in Part 1. The annualized change from baseline in log10 transformed htTKV will be summarized by treatment cohort for all participants in the P2EAS. Anti-log of the mean annualized change from baseline in log10 transformed htTKV will provide an estimate of the geometric mean of the related growth of htTKV to baseline htTKV (i.e., 100% plus annualized percent change).

The annualized percent change from baseline in htTKV in Part 2 will be presented by treatment cohort and overall for participants in the P2EAS along with the annualized percent change from baseline at Part 1 for the participants in each treatment cohort.

The above comparison will also be performed by replacing the log10-transformed htTKV value at 28 days after the last dose of the study drug by the log10-transformed htTKV value at 28 days after Week 104.

8.10. Health Outcome Analyses (Part 2)

The descriptive statistics for change from baseline in each domain score of three patient reported health questionnaires are presented at each evaluated visit in Part 2 by treatment cohort and overall for all the participants in the P2EAS. Baseline score is defined as the domain score from Follow-up period I (Visit 25) after Week 52 in Part 1. In order to compare the results from Part 2 to those in Part 1, the descriptive statistics for change from baseline in each domain score of three patient reported health questionnaires are presented at each corresponding visit at Part 1 by treatment cohort.

8.11. Exploratory Comparison Analyses (Part 2)

8.11.1. Annualized Percent Change in htLV

The derivation of the annualized percent change from baseline in htLV in Part 2 and presentation of the analysis results will be the same as the analysis of htTKV described in Section 8.9.2 except that the htTKV data will be replaced by the htLV data.

8.11.2. Urine Osmolality

Descriptive statistics for the change from baseline (Visit 2) in morning spot urine osmolality will be presented for the participants in the P2EAS by treatment cohort and overall at each scheduled time point. The number (%) of participants who show suppressed urine osmolality by treatment cohort and overall, defined by two levels of spot urine osmolality \leq 250 mOsm/kg and \leq 300 mOsm/kg will be summarized descriptively at each time point.

8.11.3. Annualized Change from Baseline in eGFR (2021 CKD-EPIcr-cys_R)

The analysis of the annualized change in eGFR analysis will be the same as described in Section 8.7, except that the eGFR values used will be determined using the 2021 CKD-EPIcr-cys_R equation for serum creatinine and cystatin C.

8.12. Additional Analyses (Part 2)

Additional exploratory analyses may be conducted to address any issues caused by potentially different treatment/exposure patterns between Part 1 and Part 2 for the participants in the P2EAS.

9. Safety and Tolerability Analysis

Safety will be evaluated from reported AEs, changes in clinical laboratory values, changes in

vital signs, and electrocardiogram (ECG results).

A Safety Analyses will be performed for the following:

- Single-Blind Placebo Run-in Period for the Placebo Run-in Safety Set (Part 1)
- Lixivaptan Titration Period for the Lixivaptan Treated Safety Set (Part 1)
- Double-blind, Randomized Treatment and Follow-up I Periods for the Randomized Safety Set (Part 1)
- Maintenance Treatment and Follow-up II Periods for the P2SS (Part 2)
- Double-blind, Randomized Treatment and Follow-up I Periods and Maintenance Treatment and Follow-up II Periods for the LTSS (Part 1 and Part 2 combined)

The tolerability will be summarized by:

- Incidence of participants with the maximum dose level taken by the final tolerated dose level determined for the double-blind treatment period during Lixivaptan Titration Period
- Count and percentage of participants up-titrated, down-titrated, remaining unchanged, or discontinued by the dose levels by visit (or time after titration initiation) during Lixivaptan Titration Period
- Count and percentage of participants by dose level by Visit (or time after randomization) during the double-blind treatment period in Part 1 by treatment group
- Count and percentage of participants by dose level by Visit (or time after initiation of maintenance period) during the maintenance period in Part 2 by treatment group

